To include the options of recall coordinated from within participating practices and centralised recall coordinated by the Primary Health Organisation (PHO).

To screen at least 3000 patients using their choice of one of the following tests:

- Vaginal hrHPV self-test performed at home or other suitable location
- Vaginal hrHPV self-test performed at the General Practice (GP) clinic (with or without nurse or kaiāwhina-led support)
- Clinician-taken cervical liquid-based cytology sample.

To implement NCSP-agreed care pathways for abnormal hrHPV screening results utilising cervical cytology, colposcopy and repeat screening.

To implement NCSP-agreed screening and care pathways for patients with previous abnormal cytology.

Objectives

Primary

To describe the impact of hrHPV testing (by demographics and screening history when numbers permit) in terms of:

- Proportion of patients screened by each method
- Proportion of patients who complete or do not complete each step of the appropriate screening pathway (including uptake of screening, cytology triage, and colposcopy assessment) and referral back to primary care
- Time to completion of the appropriate screening pathway
- Screening outcomes in patients with prior abnormalities in relation to transition guideline recommendations
- Number of colposcopy referrals, their indication, and outcomes.

To describe the disease burden detected in the study population, in terms of:

- HPV positivity rate by HPV 16/18 or other hrHPV, by demographics
- Incidence of CIN2+ in patients with HPV 16/18 by cytology result
- Incidence of CIN2+ in patients and with other hrHPV with abnormal cytology.

Secondary

To describe uptake of screening by mode of invitation:

- Centralised PHO or practice-based recall.

To describe resource utilisation (e.g. number of contacts, type of contact, engagement of other agencies, cost to patient) to achieve completion of the screening pathway:

- To achieve hrHPV screen
- In the event of an abnormal hrHPV screen, to achieve cervical cytology and/or colposcopy.

To report the rate of unsatisfactory hrHPV samples or documentation.

Equity

Compared to the general population, Māori and Pacific patients are less well served by the NCSP based in traditional primary care practices. The reason for introducing the HPV self-test is to reduce the incidence of cervical cancer and reduce inequities by providing a more sensitive test and reducing barriers to cervical screening.

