- Other (e.g. unable to consent to screening, never sexually active)

*For full details of inclusion for NCSP screening, please refer to the 2020 Ministry of Health Clinical Practice Guidelines for Cervical Screening in New Zealand at www.nsu.govt.nz.

Centralised or practice-based recall

In collaboration with the involved PHO's, participating practices will determine the mode of recall utilised for their patients. This may be recall based in the practice or co-ordinated regionally by PHOs.

Identification of eligible patients

All patients enrolled in participating practices eligible for screening according to NCSP guidelines who are due or overdue for a screen within the study timeframe will be considered eligible to participate in the study.

Eligible patients will be identified from the following sources:

- National Screening Unit (NSU) monthly report
- Practice recall registry
- Practice patient information system (eligible but not enrolled including patients over 24.5)
- Opportunistic drop in of unscreened but eligible patients or patients due for a screen who would otherwise be eligible.

A list of eligible patients, date of birth, ethnicity, date of last screen, and date of screen will be kept by participating practices and/or PHOs. The number and date of attempts to contact patients will also be recorded.

Identified data collected for participating patients and deidentified data collected for non-participating patients will be analysed centrally.

Practice-based recall and recruitment

A lead screener will be identified in each practice. Recall practice will be determined by the participating practice however at a minimum will include the following safeguards.

- Patients who are eligible be identified as above. If eligible they will be sent a written invitation (letter or email) and/or a text invitation to undergo screening and offered enrolment in the pilot study.*
- If patients do not respond, a second and, subsequently, a third invitation by letter, email text and/or direct contact.
- Any further intervention to enrol will be determined by the standard practice of that provider. This includes the option to use a poster, as approved by the Health and Disability Ethics Committee.
- Referral to screening support services may also occur consistent with individual practices.

The number of attempts and nature of these attempts will be documented.

The NSU will also be informed of patients that remain underscreened.

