Data from participating patients will be collected within participating practices and from the central study site on a secure web-based REDCap database stored on a secure University of Otago server.

Data sources include practice screening registry, NCSPR, consent, practice records, and laboratory results (cytology, histology, hrHPV, colposcopy records). Data will be anonymised prior to analysis.

Specimen storage /disposal

Specimen storage /disposal will be as per NCSP/ laboratory protocol (please see Tissue Management Plan for detail).

Outcome measures

HrHPV TESTING
The number (and percentage) of participants with: 1,2,3 or >3 attempts to be contacted prior to their hrHPV test.
The mean, median and range for time from the first study appointment to an hrHPV test being conducted, for each participant.
The mean, median and range for time from the first contact attempt to an hrHPV test being conducted, for each participant.
The number (and percentage) of participants who were successfully contacted to take part in the study by: 
 - Letter - Text - Opportunistic invitation at their GP clinic - A face to face appointment with a staff member at their GP clinic - A phone call with a staff member from their GP clinic - Other form of contact.
The mean, median and range for the time from the first study appointment to an hrHPV test being conducted, for each participant.
The mean, median and range for the time from an hrHPV test being undertaken to being received by the laboratory for analysis, for each participant.
The number (and percentage) of participants that undertook a: 
 - Vaginal test at home - Vaginal test at their GP clinic without staff assistance - Vaginal test at their GP clinic with staff assistance - Cervical test without concurrent cytology - Cervical test with concurrent cytology.
The mean, median and range of charges (NZD) for each type of hrHPV test listed under the outcome above. This will be reported by whether the tests were subsidised or not.
The mean, median and range for the time from an hrHPV test to the results report being issued.

UNSATISFACTORY hrHPV TESTS
In participants who underwent hrHPV testing and had an unsatisfactory result, the reason for that result: 
 - Incorrect labelling - Sample unsatisfactory

HPV-based Screening Implementation Study Protocol

- Other

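### The contact outcomes cover only people who were tested or reached, so on their own they cannot give the contacts needed to achieve an hrHPV screen

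*Protocol*

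**What the plan says.** The Protocol's secondary objectives (Objectives, Secondary) include "To describe resource utilisation (e.g. number of contacts, type of contact, engagement of other agencies, cost to patient", among other items, and one of the two endpoints named for that effort is achieving an hrHPV screen.

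In Outcome measures, the hrHPV testing table serves this objective with two items:

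- the number and percentage of participants with "1,2,3 or >3 attempts to be contacted prior to their hrHPV test";
- "The number (and percentage) of participants who were successfully contacted to take part in the study by" letter, text, opportunistic invitation, face-to-face appointment, phone call or another form.

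The only outcome for non-participants is the last item under Other in the same section. It gives their number and whether or not they had cytology in the screening period, with no attempts and no mode.

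Data capture is wider than the outcome list. Identification of eligible patients describes a list of eligible patients kept by practices or PHOs and adds: "The number and date of attempts to contact patients will also be recorded". The same section says that "deidentified data collected for non-participating patients will be analysed centrally", without giving their content. Practice-based recall and recruitment adds: "The number of attempts and nature of these attempts will be documented". Centrally-coordinated recall has no matching sentence on the nature of attempts.

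**The concern.** Both contact outcomes condition on success. A person who was invited several times and never screened contributes to neither. A participant who consents but never returns a home kit also falls outside the attempts item, because that item counts attempts before a test.

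The people left out absorb much of the effort. Under practice-based recall, a non-responder gets a second and then a third invitation. Under central recall, a non-responder is approached at least three times unless they ask for contact to stop. A recall service planning the national roll-out needs total contacts divided by completed screens, and the listed outcomes supply only part of the numerator.

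The gap is not equal across groups. Outcomes are to be shown by ethnicity, deprivation and region where numbers permit. A group with lower uptake has more unscreened people per screened person, so more of its effort goes unseen. Those are the groups for which the study wants to learn where resources are needed.

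The mode item has a related limit. It shows how the people who were reached were reached. It has no denominator of people tried by each mode, so a mode used on everyone can take a large share of contacts whatever its yield.

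**Working it through.** **Denominators set side by side (Protocol, Outcome measures)**

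| Step | Population for the count of attempts or invitations |
|---|---|
| hrHPV test | participants, before their test |
| Cytology | participants recommended to have cytology |
| Colposcopy | participants referred for colposcopy |

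The two later steps count everyone who needed the step. Only the first step counts those who completed it.

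**The plan's own figure (Statistical Considerations)**

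- Eligible per average practice: 1600. Due in 6 months: 1600 / 3 / 2 = 266.7, given as 266.
- Participating at 75%: 266 × 0.75 = 199.5, given as 200.
- Over 15 practices: 199.5 × 15 = 2992.5, against the stated 3000. The target reproduces.
- Non-participants: 266 × 15 × 0.25 = 997.5, or one for every three participants.

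**Effort per completed screen**

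Let m be the mean attempts per screened person, k the mean attempts per unscreened person, and r the ratio of unscreened to screened people.

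- All-in effort per completed screen: E = m + k × r.
- Shortfall if m is read as the answer: 1 − m / E.

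The Protocol's 25% gives r = 1/3. It gives neither m nor k. I assume m from 1 to 2, and k from 1 (an early decliner) to 3 (the third invitation to a non-responder).

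| k | m | E | Shortfall |
|---|---|---|---|
| 1 | 1 | 1 + 1/3 = 1.33 | 25% |
| 1 | 2 | 2 + 1/3 = 2.33 | 14% |
| 2 | 1 | 1 + 2/3 = 1.67 | 40% |
| 2 | 2 | 2 + 2/3 = 2.67 | 25% |
| 3 | 1 | 1 + 1 = 2.00 | 50% |
| 3 | 2 | 2 + 1 = 3.00 | 33% |

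The range is 14% to 50%. The attempts left out run from 1 × 997.5, about 998, to 3 × 997.5, about 2992.

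**Lower uptake**

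Assume 50% uptake, so r = 1. At k = 1 and m = 2, E = 3.0 and the shortfall is 33%. At k = 3 and m = 1, E = 4.0 and the shortfall is 75%.

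**Two groups with the same participant table**

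Take m = 1.5 in both groups.

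- 75% uptake: E = 1.5 + k/3, which is 1.83 at k = 1 and 2.5 at k = 3.
- 50% uptake: E = 1.5 + k, which is 2.5 at k = 1 and 4.5 at k = 3.

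The participant table would look alike for both.

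**The case against.** The strongest reply is that the Protocol never defines contacts per completed screen. It lists a distribution of attempts among participants and labels it as such. The study is stated to be non-comparative and largely descriptive, and the resource objective could be read as effort among those who completed the step. This stands in part: the table is correct for what it describes, and the shortfall arises only when it is used to answer the objective. But the objective asks what it takes to achieve a screen, the study's goal is to follow the pathway from invitation, and the later steps use the wider denominator.

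A second reply is that the detail may sit in a statistical analysis plan or the separate Data Management Plan, neither of which is at hand. That would answer a missing detail. Here the Protocol itself states the population for each outcome.

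Three stronger readings are tempting, and the documents do not support them.

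- A reader might infer that non-responder data are collected and then discarded. The Protocol does not say so. It says that non-participant data will be analysed centrally and leaves open what will be reported.
- A reader might infer that a biased success rate by contact mode is planned. No such rate is planned. The only uptake comparison by invitation is central against practice-based recall, and invitations can combine modes.
- A reader might give every non-participant three attempts and quote a single figure near the top of the range. The 25% is an assumed share who do not wish to take part. Under central recall, contact stops on request, people with off-study cytology get no further invitations, and some will decline when asked opportunistically. So k may be well below 3.

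**Conclusion.** The point holds as a mismatch between a stated objective and the populations fixed for its outcomes. The direction does not depend on assumptions beyond some contact having been made with unscreened people. The 14% to 50% does: it takes 25% non-participation from the Protocol and assumed values of m and k, so it is an illustration and not a documented error. It widens if uptake falls below 75%.

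The point deserves correction because the objective cannot be met from the listed outcomes alone, and because the gap is larger in lower-uptake groups. No primary objective, sample size or safety outcome depends on it.

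**What to change.** 1. In Outcome measures, report the number of contact attempts for all invited eligible patients by final status: screened in the study, off-study cytology, declined, no response. Show participants who consented but had no test as a separate line.
2. Report total attempts divided by completed screens, overall and by recall type, and by the planned demographic groups where numbers permit. Work from the recorded counts, because the open category above 3 does not allow a total.
3. Add contact mode on the same denominator where it is recorded. Confirm whether the nature of attempts is captured under central recall, which covers the five Whanganui practices.
4. Label the existing mode table as describing how participants were reached, not which mode works.

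Cost: a small extra tabulation. The number and date of attempts are already to be recorded for the eligible list. What has to be confirmed is that the counts are part of the de-identified non-participant data sent for central analysis. Mode under central recall may need one more recorded field.
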